### **3.3 OUTCOME MEASURES**

#### **3.3.1 Primary Outcome Measure**

The primary outcome measure for safety and tolerability is the following:

Incidence and severity of ocular and systemic adverse events. Examples include 30 letter loss, major subretinal hemorrhage, involving 75% or more of clinical macula (arcade to arcade), disease-related vitreous hemorrhage, injection-related endophthalmitis, retinal detachment, vitreous hemorrhage, *study drug/procedure* -

related uveitis, incidence and severity of other adverse events, as identified by physical examination, subject reporting, and changes in vital signs.

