### **Secondary Outcome Measures**

- Month 3, 6, 9, 12 best corrected visual acuity at 4 meters – rates for gain of 5,10 and 15 or more letters
- Month 3, 6, 9, 12 best corrected visual acuity at 4 meters- rates for loss of 15 or more letters
- Median and Average best corrected visual acuity at 4 meters- gain/loss (letters) at 3,6,9,12 months.
- Mean change from baseline in central foveal thickness over time up to 12 months as assessed on OCT
- Mean change from baseline in macular volume overtime up to 12 months.
- Proportion of patients with no evidence of fluid from CNV as assessed by OCT at 12 months.
- Mean change from baseline in the total area of CNV fluorescein angiographic leakage overtime up to 12 months.
- Mean change from baseline in total area of ICG CNV lesion size (including polyps and deep choroidal vessels) overtime up to 12 months.
- Fluorescein and ICG angiograms and fundus photographs will also be graded at each time point compared to baseline as unchanged, resolved, improved, worsened, or cannot determine. For the FA and ICG evaluations, “resolved” will be defined as no leakage and no evidence of polyps or PCV choroidal lesion; “improved” will be defined as decreased leakage and/or decreased size, number, or hyperfluorescence of polyps and/or PCV choroidal lesion; and “worsened” will be defined as increased leakage and/or increased size, number or hyperfluorescence of polyps and/or PCV choroidal lesion. For fundus photography evaluations, “resolved” will be defined as no evidence of PED, subretinal fluid, hemorrhage, or hard exudate; improved will be defined as a decrease in PED,

subretinal fluid, hemorrhage, or hard exudate; and “worsened” will be defined increase in PED, subretinal fluid, hemorrhage, fibrosis, or hard exudates.

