## 4.8 STATISTICAL METHODS

### 4.8.1 Analysis of the Conduct of the Study

There is no formal sample size calculation in this pilot study. As this is a phase I study, a sample size of 20 patients is chosen, making sure that it is feasible financially to conduct the study and logically to complete the study within 2-3 years. If and when the study is planned for a phase II randomized control trial, appropriate statistical analysis will be determined.

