### 4.8.3 Efficacy Analyses

1. **Primary Endpoint-** See Section 3.3.1

2. **Secondary Endpoints-** See Section 3.3.2

All subjects will be used in analysis of primary and secondary outcome parameters. Rates for the endpoints at the suggested time points will be presented as a % of the patients enrolled. Analysis of Variance will be used to assess for role of variables in for the endpoints. Variables will include # Ranibizumab injections, other therapies, baseline acuity, age, gender, etc.

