### **5.1 ADVERSE EVENTS**

*All adverse events occurring from Day 0 through Month 12 or Early Withdrawal will be documented and assessed by the principal investigator.* Subjects discontinuing early from the study should return for an early termination evaluation and will be contacted 7 days after their last injection or study visit to elicit for occurrence of adverse events (serious and nonserious).

For this protocol, an AE is any “on study” untoward medical occurrence (e.g., sign, symptom, disease, syndrome, intercurrent illness) that occurs in a study subject, regardless of the suspected cause. “On study” refers to Day 0 through the last study visit.

Unchanged, chronic conditions are NOT AEs and will not be recorded. An exacerbation or worsening of a chronic condition should be recorded as an AE.

Both serious and nonserious AEs should be graded on a three-point scale (mild, moderate, severe) and reported in detail in the subjects clinic record.

The suggested definitions are as follows:

Mild: Discomfort noticed but no disruption of normal daily activity

Moderate: Discomfort sufficient to reduce or affect normal daily activity

Severe: Incapacitating with inability to work or perform normal daily activity

Using the following criteria, the investigator will also assess whether there is a reasonable possibility that study drug caused or contributed to the AE.

- Yes (possibly or probably)

There is a clinically plausible time sequence between onset of the AE and study drug administration; and/or

There is a biologically plausible mechanism for study drug causing or contributing to the AE; and

- No

The AE may or may not be attributed to concurrent/underlying illness, other drugs, or procedures.

A clinically plausible temporal sequence is inconsistent with the onset of the AE and study drug administration; and/or

A causal relationship is considered biologically implausible.

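### Section 4.8.3 names ANOVA as its only method for every endpoint; for yes/no and graded outcomes in 20 subjects its p-values are unreliable when events are few and a factor level is sparse

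*Combined protocol and SAP*

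**What the plan says.** Section 4.8.1 states that "There is no formal sample size calculation in this pilot study" and that "a sample size of 20 patients is chosen", on grounds of feasibility. Section 4.8.3 identifies its endpoints by pointing to Sections 3.3.1 and 3.3.2. It states that "All subjects will be used in analysis of primary and secondary outcome parameters", that rates will be shown as percentages of those enrolled, and that "Analysis of Variance will be used to assess for role of variables in for the endpoints". The explanatory variables are listed with an open end: "Variables will include # Ranibizumab injections, other therapies, baseline acuity, age, gender, etc".

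The outcomes so covered are of three kinds:

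- **Yes/no:** the incidence part of "Incidence and severity of ocular and systemic adverse events" (Section 3.3.1); gains of 5, 10 and 15 letters; "rates for loss of 15 or more letters"; and absence of fluid on OCT at 12 months.
- **Graded:** adverse event severity on three levels (Section 5.1), and the angiographic and photographic grades, which include a cannot-determine category.
- **Continuous:** changes in letters, central foveal thickness, macular volume, leakage area and lesion area.

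No exact, logistic or rank-based method appears in Section 4.8. Nor does an alpha level, a multiplicity rule or a statement that these analyses are exploratory.

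**The concern.** ANOVA compares means and assumes a roughly continuous outcome with similar variance in each group. For a 0/1 outcome the variance depends on the event rate. When all the events sit in one small group, the within-group variance that forms the denominator of F becomes very small. A single subject can then produce a small p-value.

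The outcomes most exposed are those with the fewest events, such as adverse events and loss of 15 letters. Sparse levels are plausible for two of the named variables. Section 3.1 suggests PDT, laser or steroids only after a 10-letter loss, two consecutive injections and persistent OCT activity, so few subjects may receive any one of them. Injection counts can spread from 3 upwards, leaving few subjects at each count. A chance placement of one event could then be read as a role for that variable, in a pilot that may inform a phase II trial (Section 4.8.1).

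**Working it through.** The plan has no figure to reproduce, since the sample size comes from no formula. The check is of the named test itself.

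**Inputs.** n = 20 (Section 4.8.1). Outcome coded 0/1. Factor level of size k against the other 20 − k. Two-sided alpha of 0.05, assumed. The documents do not give the frequencies of other therapies or injection counts, so k is varied.

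**Step 1: one event, falling in the level of size k.** The overall mean is 1/20. The between-group sum of squares is 1/k − 1/20 and the within-group sum is 1 − 1/k, on 1 and 18 degrees of freedom. Hence

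F = 18(20 − k) / [20(k − 1)].

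For k = 2: 18 × 18 / 20 = 16.2. For k = 3: 18 × 17 / 40 = 7.65. For k = 4: 18 × 16 / 60 = 4.8. The two-sided Fisher p-value for k below 10 is k/20.

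| k | F | ANOVA p | Fisher p |
|---|---|---|---|
| 2 | 16.2 | 0.0008 | 0.10 |
| 3 | 7.65 | 0.013 | 0.15 |
| 4 | 4.8 | 0.042 | 0.20 |
| 5 | 3.375 | 0.083 | 0.25 |
| 7 | 1.95 | 0.18 | 0.35 |
| 10 | 1.0 | 0.33 | 1.0 |

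At k = 1 the within-group variance is zero and F is infinite.

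**Step 2: false-positive rate given the number of events.** With no association, one event falls in the level with probability k/20. ANOVA therefore gives p < 0.05 in 2/20 = 10%, 3/20 = 15% and 4/20 = 20% of cases for k = 2, 3 and 4, and never for k = 5, 6, 8 or 10, or for k = 7. Fisher never does with one event.

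With two events the pattern is uneven:

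- k = 2: 19.5% (Fisher 0.5%).
- k = 3: 1.6% (Fisher the same).
- k = 7: both events fall in the level with probability (7 × 6)/(20 × 19) = 11%. ANOVA p is then 0.044 and Fisher p is 0.11.

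**Step 3: averaged over event counts.** The conditional rates are weighted by binomial probabilities for event rates of 1.9%, 5%, 10%, 15% and 30%. The 1.9% is the first-year arterial thromboembolic rate on 0.3 or 0.5 mg in Section 1.5; the others are assumptions. As an example, take a rate of 1.9% and k = 2. No event occurs with probability 0.981^20 = 68%, exactly one with 26.4%, and exactly two with 4.9%. The error is about 0.264 × 0.10 + 0.049 × 0.195 = 3.6%. Over the whole range, levels of 2-4 give about 4-9% and a level of 7 gives 0.6-4.4%.

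**Step 4: by variable, given one event.**

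- Sex: the sponsor's previous cohort (Section 1.3) had 12 women and 4 + 3 = 7 men. With k = 7 of 20, p = 0.18, so one event cannot reach 0.05.
- Age or baseline acuity entered linearly (simulated, normal covariate): 4.8%.
- Injection count as a factor, assumed uniform over 3-12 (simulated): about 14%. Entered as a linear term: 1.1%.

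**The case against.** The strongest reply is that this is one underspecified sentence in an uncontrolled pilot. Section 4.8.2 says safety data will be summarised, Section 5 relies on rates, and Section 4.8.3 itself presents rates first. No hypothesis or significance claim is made anywhere. This stands as far as it goes: the safety conclusion need not rest on an ANOVA p-value. It does not remove the point, because Section 4.8.3 expressly brings the primary outcome in through Section 3.3.1 and names no other method.

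Three stronger readings are tempting, and the documents do not support them.

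- A reader might infer that one event could appear as an effect of sex or age. For a sex split like the previous cohort's it cannot, and for age entered linearly the error is nominal. Sparse levels are needed, and how sparse the levels will be is not stated.
- A reader might infer that the test is badly wrong in general. The 10-20% rates hold given exactly one event. Averaged over event counts the excess is modest, and for some combinations ANOVA rejects less than 5% of the time. The average is still no comfort to someone reading a single dataset with one event in a level of 2, where ANOVA reports 0.0008 and the exact value is 0.10.
- A reader might take the number of tests as evidence against ANOVA. In a simulated five-variable model with one event, about 17% of endpoints show at least one p < 0.05. Five independent valid tests would give 1 − 0.95^5 = 22.6%. That is multiplicity, which any correct test shares.

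It is also fair to say that Fisher's test cannot fall below 0.05 with one event, so counts with intervals carry more information. And injection count and other therapies follow partly from acuity loss and OCT activity (Section 3.1), so their role is hard to interpret whichever test is used. Both are accepted.

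**Conclusion.** The concern holds in a limited form. As written, Section 4.8.3 applies ANOVA to yes/no and graded outcomes for which it is unsuitable in 20 subjects, and offers nothing else. The p-value is unreliable where few events meet a factor level of about 4 or fewer subjects, and in certain other combinations such as two events with a level of 7. This rests on an assumed alpha of 0.05 and on sparse levels actually occurring, which is plausible for other therapies and for injection count treated as a factor. ANOVA remains suitable for the continuous changes. Not every yes/no endpoint will be rare: in the previous cohort 4 of 14 eyes gained at least 3 lines at 12 months. The change is worth making because it is specific and needs wording only.

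**What to change.** Amend Section 4.8.3 as follows:

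- Limit ANOVA and linear models to the continuous changes: letters, thickness, volume, leakage area and lesion area.
- Report adverse events and the other yes/no endpoints as counts with exact 95% confidence intervals. For scale, 0 of 20 gives 0% to 16.8% and 1 of 20 gives 0.1% to 24.9%.
- Where an association is examined for these endpoints, use Fisher's exact test for categorical variables and exact or Firth logistic regression for continuous ones, one variable at a time.
- Use a rank-based method for the angiographic and photographic grades, with cannot-determine treated as missing and counted separately.
- Replace the open end of the variable list with a fixed list, and say for each variable whether it enters as a category or as a continuous term.
- Label these analyses exploratory and state how many tests were done.

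The cost is wording; no visit, measurement or sample size changes. The downside is that exact methods are conservative, so fewer associations will reach nominal significance.

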#### 4.1.2 **Inclusion Criteria**

Subjects will be eligible if the following criteria are met. *Any deviation/waivers granted regarding inclusion/exclusion criteria will be reviewed by the principal investigator and fully documented.*

- Males and Females >18 years of age. *Females of child bearing potential will undergo urine pregnancy testing* and be required to use appropriate methods of birth control.
- ICG and fluorescein angiographic characteristics consistent with active, leaking PCV with subfoveal lesions &/or subfoveal hemorrhage, lipid exudates, PED or fluid diagnosed within the past 6 months or diagnosed as newly active within the past 6 months. Subjects who completed the 24 month follow up in the original FVF3671s protocol may enter the extension study with 2.0 mg without necessarily demonstrating active exudative PCV at enrollment.
- Best-Corrected ETDRS Visual Acuity at 4 meters between 20/20 – 20/800
- Lesion size- no limitations
- Lesion Characteristics- leaking lesions consistent with PCV. No limitations on hemorrhage, fibrosis or atrophy.
- No therapy (includes non foveal laser, PDT, intravitreal steroids, TTT, radiotherapy, or anti-VEGF therapy) or intraocular surgery within the past 30 days for any condition.

- Clear ocular media to allow for photography/angiography.
- Ability to provide written informed consent and comply with study assessments for the full duration of the study

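### Section 4.8.3 assesses baseline acuity as a predictor of change from that same baseline, which biases its term, and applies an open-ended list of predictors to all endpoints in 20 subjects without an exploratory label

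*Combined protocol and SAP*

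**What the plan says.** Section 4.8.3 states: "Analysis of Variance will be used to assess for role of variables in for the endpoints". It then gives the list: "Variables will include # Ranibizumab injections, other therapies, baseline acuity, age, gender, etc". That is five named variables and an open end. The section points to the primary and secondary outcome measures and does not say which endpoints, visits or models are meant.

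Under Secondary Outcome Measures (Section 3.3), the acuity outcomes at Months 3, 6, 9 and 12 are "rates for gain of 5,10 and 15 or more letters", the rate of loss of 15 or more letters, and "Median and Average best corrected visual acuity at 4 meters- gain/loss (letters) at 3,6,9,12 months". All are changes from baseline. The other secondary outcomes are changes in foveal thickness, macular volume, leakage area and lesion area up to Month 12, absence of fluid at Month 12, and graded angiograms and photographs.

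The entry range in Section 4.1.2 is wide: "Best-Corrected ETDRS Visual Acuity at 4 meters between 20/20" at the better end and 20/800 at the worse end. On numbers, Section 4.8.1 says "There is no formal sample size calculation in this pilot study" and "a sample size of 20 patients is chosen". Section 4.8.4 uses available cases, so fewer than 20 may be analysed. Section 4.8 gives no significance level, multiplicity rule or exploratory label for the predictor analyses.

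**The concern.** There are two separate problems.

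First, change is follow-up minus baseline, so baseline enters the outcome with a minus sign. An eye measured on a bad day at baseline tends to score better later even if nothing has changed. At the ends of the scale, an eye near 20/20 has little room to gain and an eye near 20/800 has little room to lose. All three mechanisms make better-starting eyes appear to gain less and lose more, even when true benefit is unrelated to starting vision.

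Second, five or more variables across many correlated endpoints and visits in 20 subjects will usually produce some apparent predictors by chance. Nothing in the plan tells the reader to discount them.

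At stake is how the secondary results are read, in particular a statement that eyes with poorer vision benefit more. The primary safety outcome is not affected.

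**Working it through.** The plan has no alpha, power or effect-size figure to reproduce. Everything below assumes a two-sided 0.05 per test.

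**1. Coupling when all lost correlation is error or fluctuation.** With equal variances at baseline and follow-up and correlation r, corr(baseline, change) = -sqrt((1-r)/2). Simulated rejection rates at n = 20, with benefit unrelated to baseline:

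| r (assumed) | corr(baseline, change) | p < 0.05, letter change | p < 0.05, gain of 15 letters |
|---|---|---|---|
| 0.9 | -0.22 | 16% | 9% |
| 0.8 | -0.32 | 28% | 16% |
| 0.7 | -0.39 | about 40% | 24% |
| 0.5 | -0.50 | 64% | 40% |

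This is a demanding assumption. With a baseline SD of 20 letters, the error or fluctuation SD at each visit would have to be 20 × sqrt(1-r), which is 6.3, 8.9, 11.0 and 14.1 letters for r = 0.9, 0.8, 0.7 and 0.5.

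**2. Coupling when only modest measurement error is at work.** Let true acuity have SD 20, measurement error SD e at each visit, and true benefit SD s, independent of baseline. Then corr(baseline, change) = -e² / sqrt((400 + e²)(s² + 2e²)).

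| e (letters) | s = 0: corr, p < 0.05 | s = 16: corr, p < 0.05 |
|---|---|---|
| 3 | -0.11, 7% | -0.03, 5% |
| 5 | -0.17, 11% | -0.07, 6% |
| 8 | -0.26, 20% | -0.15, 10% |

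The range is therefore about 5-20%. Adding the limits of the letter scale raised its top only to about 22%.

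**3. What the site's earlier study implies (Section 1.3).** Letters are converted as 85 + 50 × log10(Snellen fraction), an assumption.
- Baseline 20/16 to 20/500 is 89.8 - 15.1 = 74.7 letters. The expected range of 20 normal values is 3.73 SD, so the SD is about 74.7/3.73 = 20.0.
- A mean gain of 1.2 lines is about 6 letters, and 4 of 14 eyes gained 3 lines. The SD of change is about (15 - 6)/0.566 = 15.9.
- With equal variances, r is about 1 - 15.9²/(2 × 20.0²) = 0.68 to 0.69, which in step 1 means a rate of roughly 40%.

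This rests on few eyes. It also cannot separate error from real differences in benefit: if the spread of change is mostly real, the s = 16 column applies instead.

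**4. Ends of the scale.** On the same conversion, 20/20 is 85 letters and 20/800 is about 5. A 15-letter gain from 20/20 needs a score of 100. An eye with 5 letters cannot lose 15.

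**5. Number of tests.** Expected chance findings = analyses × 5 variables × 0.05. The plan does not fix the visits, so several counts are shown.

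| Reading | Analyses | Tests | Expected |
|---|---|---|---|
| Ten endpoints at Month 12 only | 10 | 50 | 2.5 |
| Acuity at four visits (20), other five at Month 12 | 25 | 125 | 6.25 |
| Acuity (20), four imaging means at four visits (16), no fluid (1) | 37 | 185 | 9.25 |
| As above plus three graded image types at four visits | 49 | 245 | 12.25 |
| Acuity (20), monthly OCT measures (24), no fluid (1), areas and grades at six visits (12 + 18) | 75 | 375 | 18.75 |

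On the 185-test count, 20 tests relate baseline acuity to acuity change and are not null tests. Without them the figure is 165 × 0.05 = 8.25. At alpha 0.01 or 0.10, 185 tests give 1.85 or 18.5. A simulated global null with 37 endpoints correlated at 0.5 gave a mean of 9.4, a median of 7, a 5th to 95th percentile range of 1 to 26, and at least one finding in 96% of trials.

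**The case against.** The best defence is that this is an uncontrolled Phase I safety pilot. The primary outcome is adverse events, endpoint rates are reported as percentages, and no hypothesis test, alpha or p-value is promised. The predictor analyses support no primary conclusion. That stands, and it limits the importance of the point. It does not remove the point, because the plan says it will assess the role of each variable and gives no caution about reading the result.

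Four stronger readings are tempting and are not supported.
- **Baseline acuity is bound to look important.** The bias is in direction. Over most of the plausible range a false significant result is the less likely outcome, and with modest error and varying benefit the rate is close to nominal.
- **About nine false findings will appear.** That needs an alpha the plan does not state and one particular tally. Section 4.8.3 does not say that every variable is tested at every visit. The upper counts include image grades, which are categories with a cannot-determine level and do not fit ordinary analysis of variance directly.
- **Spurious predictors will shape a phase II trial.** Section 4.8.1 says only that a suitable analysis would be determined if such a trial is planned. It mentions neither eligibility nor stratification.
- **Oldham's method is the cure.** Relating change to the mean of baseline and follow-up holds its 5% level when variances are equal. If benefit varies between eyes independently of baseline, follow-up variance is larger and the method creates a positive association. With benefit SD 16 and error SD 3-8 letters it rejected in about 25-35% of null trials, against 5-10% for the planned comparison.

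**Conclusion.** The point holds in a limited form. Followed as written, Section 4.8.3 yields a baseline-acuity term that is biased in a known direction for every letter gain or loss outcome and cannot be read as evidence that benefit depends on starting vision. The false-positive rate may be near nominal or well above it, depending on how much of the visit-to-visit variation is error; the documents do not settle this. The open list of predictors makes at least one chance finding very likely on most readings, but the number is uncertain. The rates assume n = 20, normal data and a two-sided 0.05, and the letter-scale steps assume the conversion shown. With fewer available cases, the coupling rejection rates fall somewhat (for r = 0.7, about 33% at n = 16), but the direction of the bias does not change. This is a defect in secondary analyses that wording can repair.

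**What to change.** In Section 4.8.3:
- Use baseline acuity only as an adjusting covariate in a model for follow-up acuity, and do not test or interpret its term for change, gain or loss outcomes. In a linear model, the coefficients of the other variables are the same whether the outcome is follow-up acuity or change.
- Limit predictor models to Month 12 acuity change and Month 12 thickness change, with one or two baseline variables named in advance, and delete *etc.*
- Report estimates with 95% intervals and label these analyses exploratory.
- Do not make Oldham's method the default. If dependence on starting acuity is of interest, show baseline against Month 12 acuity, report the two variances, and state the limitation.

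The cost is a paragraph of wording and fewer exploratory results. Number of injections and other therapies arise after baseline, so they leave the models and would be described instead. Subjects, visits, measurements and the safety analysis are unchanged.
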